7. STATISTICAL ANALYSES

7.1. Subject Disposition

The number of subjects included in each study population will be summarized by treatment region (ie, buttocks, thighs) and overall. Subjects excluded from the Safety Population or Evaluable Population will be listed.

The frequency counts and percentages of subjects screened, screen failed, treated, not treated completed, and discontinued from study treatment and/or withdrawn from the study, as well as the reason for discontinuation from study and reason for discontinuation of study drug will be summarized by treatment region and overall.

A listing of disposition for all subjects will be provided. Screen failure reasons will also be listed. In addition, a listing for inclusion/exclusion criteria will also be presented.

7.2. Protocol Deviations

A listing of all protocol deviations will be presented.

7.3. Demographics and Baseline Characteristics

Demographic and other baseline characteristics will be summarized by treatment region, not treated and overall using the Safety and Evaluable Population.

Age, height (at screening), body weight (at screening) and BMI in kg/m² will be summarized by treatment region and overall as continuous variables using descriptive statistics. Gender, race, ethnicity, skin category based on the Fitzpatrick scale assessment, PR-PCSS, CR-PCSS, Hexsel CSS total score and report of tobacco and alcohol use (never, current, and former) will be summarized by treatment region, not treated and overall as categorical variables using frequency counts and percentages.

All demographic and baseline characteristics will be presented in a listing for all subjects.

7.4. Medical and Surgical History

Medical history will be coded using the MedDRA dictionary (version is defined in the Data Management Plan). Medical, surgical and EFP history data will not be summarized; however, a subject listing will be provided for all subjects.

7.5. Prior/Concomitant Medications and Procedures

Prior and concomitant medications, procedures and EFP treatments will be summarized by treatment region, not treated and overall using frequency counts and percentages for subjects in the Safety Population, by active ingredient within each ATC, with ATC and active ingredients ordered alphabetically. Multiple use of the same medication by a subject will be counted only once.

A listing of prior and concomitant medications and procedures will be provided for all subjects. Similarly, a separate listing of medications and procedures for EFP/Cellulite will also be presented.

7.6. Efficacy Analyses

Efficacy parameters will be summarized by treatment area (left or right) and treatment region (buttock or thigh) using the Evaluable Population.

PR-PCSS, CR-PCSS and Hexsel CSS total score ratings and the level of change from baseline will be summarized as per below sections.

A listing for digital photography will be provided with date and time for photos taken and reasons for photos not taken per protocol.

Individual listings will be provided for PR-PCSS ratings, CR-PCSS ratings and Hexsel CSS ratings and total scores.

7.6.1. Primary Endpoint

7.6.1.1. Change from Baseline in PR-PCSS Rating at Day 71

The baseline PR-PCSS ratings and the level of change in PR-PCSS ratings from Baseline (Screening) at Day 71 will be summarized using frequency counts and percentages for each severity rating and with mean and SD.

To assess the impact of CCH at Day 71, the PR-PCSS ratings at Day 71 will be compared with Baseline ratings using paired *t* test. The normality assumption of the difference of assessment will be evaluated using Shapiro-Wilk test and Q-Q plot.

Two-sided *p* value with 5% level of significance will be used to check if normality is achieved or not. Normality will be concluded if the *p* value > 0.05.

In case normality assumption is not met then Wilcoxon Signed Rank Pratt Lehmann test (adjusted for the correction factor for ties and zeros, if present) will be used.

The result of the analysis will be presented as:

SAS appendix will be presented detailing the test of normality of differences in Day 71 and Baseline PR-PCSS ratings.

Paired *t* test: Mean difference between Baseline and Day 71 ratings and associated 95% CI, SE, and *p* value. The negative mean difference indicates improvement in cellulite severity at Day 71.

Wilcoxon Signed Rank Pratt Lehmann test: Sum of positive ranks, sum of negative ranks and *p* value will be presented. If the sum of the negative rank is greater than the sum of positive rank, then it indicates improvement in cellulite severity at Day 71.

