3.3. Treatment Region

Treatment region is defined as both buttocks or both thighs. Approximately 12 subjects will be dosed in this study, thus 6 subjects will be treated in the buttocks and 6 subjects will be treated in the thighs.

No subjects will be treated in both the buttocks and the thighs.

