3.12.2.1. Patient Reported Photonumeric Cellulite Severity Scale (PR-PCSS)

The PR-PCSS-Buttock and PR-PCSS-Thigh will be used to assess the severity of cellulite of both treatment areas (each buttock and each thigh) independently.

The scale is a 5-level photonumeric scale developed specifically for patients and used by the subject to assess the severity of their cellulite in the buttocks or thighs by viewing digital images of each of their buttocks and/or thighs at Screening, Day 22, Day 43, Day 71, Day 161, and Day 251.

The ratings range from 0 (None) to 4 (Severe) with labels and descriptors to aid the subject in the assessments (Table 4).

Table 4: PR-PCSS for Buttocks or Thighs

Rating	Level of Severity	Description
0	None	No evident cellulite
1	Almost None	A few superficial dimples or ridges
2	Mild	Several dimples or ridges of which most are superficial
3	Moderate	Many dimples or ridges of which most are somewhat deep
4	Severe	A lot of dimples or ridges of which many are deep covering most of the skin area

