4.5.1. Change from Baseline in PR-PCSS Rating (Primary Endpoint)

To assess the subject reported impact of CCH in the treatment of cellulite in adult females, the change from Baseline (Screening) in PR-PCSS will be determined for treatment region (both buttocks or both thighs) on Day 71.

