6. STATISTICAL METHODS

6.1. General Methodology

All statistical analysis, summary tables and data listings will be prepared using version 9.3 or later of SAS® software.

All statistical tests of efficacy parameters will be 2-sided with a significance level of $\alpha=0.05$, unless specified otherwise.

Continuous data will be summarized using descriptive statistics (number of subjects [n], mean, standard deviation [SD] or standard error [SE], median, minimum [min], and maximum [max]) and discrete data will be summarized using frequency counts and percentages, the denominator will be based on the number of subjects in the appropriate population. For the purpose of display, the summary results will be rounded as follows:

- Min and max: same number of decimal places as the raw data.
- Mean and median: 1 more decimal place than the raw data.
- SD/SE: 2 more decimal places than the raw data.
- Percentages will be displayed with 1 decimal precision. A zero count will not have the associated percentage presented on the table (ie, no 0%).
- The standard form of a percentage change variable is 0 decimal places.

For categorical variables with missing values, a category documenting the frequency of missing values will be displayed in the summary tables.

Summary tables, subject listings and any supportive SAS output will include a “footer” of explanatory notes that will indicate, when applicable:

- Date of data extraction
- Date and time of output generation
- SAS program name, including the path, that generates the output

When calculating percentages, the denominator will be based on the number of subjects with non-missing values. If the denominator is expected to change over time, then the denominator used to calculate the percentage should be based on the number of subjects with non-missing values at each visit. Any subject removed from an analysis will be noted at the bottom of the table along with the reason the subject was removed.

Null summary tables will be presented with a note stating that “No Subjects Met Criteria”.

Subject listings of all data from the eCRFs as well as any derived variables will be presented.

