7.6.2. Secondary Endpoints

7.6.2.1. Change from Baseline in PR-PCSS Rating at Days 22 and 43

The baseline PR-PCSS ratings and the level of change in PR-PCSS ratings from Baseline (Screening) at Day 22 and 43 will be summarized using frequency counts and percentages for each severity rating and with mean and SD.

In addition, the PR-PCSS ratings at Day 22 and 43 will be compared with Baseline ratings using similar analysis as mentioned for primary endpoint. Refer to Section 7.6.1.1 for more details.

7.6.2.2. Change from Baseline in CR-PCSS Rating at Days 22, 43, and 71

The baseline CR-PCSS ratings and the level of change in CR-PCSS ratings from Baseline (Screening) at Days 22, 43, and 71 will be summarized using frequency counts and percentages for each severity rating and with mean and SD.

In addition, the CR-PCSS ratings at Days 22, 43, and 71 will be compared with Baseline ratings using similar analysis as mentioned for primary endpoint. Refer to Section 7.6.1.1 for more details.

7.6.2.3. Changes in the Hexsel CSS Total Score from Baseline at Days 22, 43, and 71

The baseline Hexsel CSS scores and the level of change in Hexsel CSS scores from Baseline (Screening) at Days 22, 43, and 71 will be summarized using frequency counts and percentages for each severity scores and with mean and SD.

In addition, the Hexsel CSS total score ratings at Days 22, 43, and 71 will be compared with Baseline using similar analysis as mentioned for the primary endpoint. Refer to Section [7.6.1.1](#) for more details.

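### SAP 7.6.1.1: a normality pretest on about six integer changes decides whether the primary result carries a planned 95% CI, and the unit of the test (side or region) is not expressly stated

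*SAP*

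**What the plan says.** **Scale and unit.** SAP 3.12.2.1 has subjects use the PR-PCSS, with whole-number ratings from 0 to 4, "to assess the severity of cellulite of both treatment areas (each buttock and each thigh) independently". Each treated subject therefore has a left and a right rating at each visit. SAP 3.3 plans about 12 dosed subjects, "thus 6 subjects will be treated in the buttocks and 6 subjects will be treated in the thighs".

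**Level of analysis.** The lead-in to SAP 7.6 reads "Efficacy parameters will be summarized by treatment area (left or right) and treatment region (buttock or thigh) using the Evaluable Population". SAP 4.5.1 says that the primary change from baseline "will be determined for treatment region (both buttocks or both thighs) on Day 71". SAP 7.6.1.1 speaks only of the ratings and does not say which of the two levels the test uses.

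**Test.** SAP 6.1: "All statistical tests of efficacy parameters will be 2-sided with a significance level of" 0.05. SAP 7.6.1.1 uses a paired t test when Shapiro-Wilk gives p > 0.05. Otherwise: "In case normality assumption is not met then Wilcoxon Signed Rank Pratt Lehmann test (adjusted for the correction factor for ties and zeros", if present).

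**Output.** On both branches, 7.6.1.1 gives frequency counts, percentages, mean and SD. The t branch adds the mean difference with 95% CI, SE and p-value. The Wilcoxon branch adds "Sum of positive ranks, sum of negative ranks and" a p-value, with no interval.

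**Reach.** For the secondary scales and visits, SAP 7.6.2 says that ratings "will be compared with Baseline ratings using similar analysis as mentioned for primary endpoint".

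**The concern.** In a 12-subject study with no formal sample size calculation (protocol 9.1, SAP 3.6), the useful primary result is an estimate with its precision. Here a pretest on about six whole numbers decides whether the planned interval is printed. Shapiro-Wilk on such data responds mainly to ties, so the outcome says little about whether a t interval is reasonable.

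Three further gaps sit in the same rule:

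- If every change in a cell is equal, neither Shapiro-Wilk nor the t test exists, and no instruction is given.
- The Wilcoxon p-value could be exact or approximate. The tie and zero correction points to the approximation, but the text does not say so.
- The unit of the test has to be inferred from two sections that point to different levels.

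At stake is whether the primary cells are reported in one form, and with how much precision.

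**Working it through.** **Inputs from the documents.** Six subjects per region (12 / 2, SAP 3.3); two rated sides per subject; integer ratings 0 to 4; two-sided 0.05; Shapiro-Wilk cut-off 0.05. The documents give no SD and no left-right correlation. Both are assumed below and shown as ranges.

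**1. One cell by hand.** Six changes: -1, -1, -1, -1, 0, 0.

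- Shapiro-Wilk p = 0.00135, so the Wilcoxon branch applies.
- Pratt ranks: the zeros take ranks 1 and 2 and are then dropped. The four tied changes each get (3+4+5+6)/4 = 4.5. Negative rank sum 18, positive 0.
- Approximation: null mean 9, variance 4 x 4.5² / 4 = 20.25, z = 9/4.5 = 2, p = 0.0455.
- Exact: 2/2⁴ = 0.125.
- Unlisted t result: mean -0.667, SD 0.516, SE 0.516/√6 = 0.211, t = -3.16, p = 0.025. CI: -0.667 ± 2.571 x 0.211, or -1.21 to -0.12.

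So significance at 0.05 depends on a choice that the SAP leaves open, and the interval that would describe the result is not listed. If five of six change by -1 and one by 0, the approximate p is 0.025 and the exact p is 2/2⁵ = 0.0625.

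**2. How often the pretest removes the interval.** Exact enumeration of all samples of six, with a normal change rounded to integers. The SD is that of the change before rounding.

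| Assumed SD | Mean change | Shapiro-Wilk p ≤ 0.05 | All changes equal | No listed CI |
|---|---|---|---|---|
| 0.6 | 0 or -1.0 | 46.4% | 4.5% | 50.9% |
| 0.6 | -0.5 | 63.2% | 1.7% | 65.0% |
| 0.8 | 0 or -1.0 | 36.6% | 1.1% | 37.7% |
| 0.8 | -0.5 | 40.7% | 0.8% | 41.4% |
| 1.0 | 0 or -1.0 | 28.4% | 0.4% | 28.8% |
| 1.0 | -0.5 | 29.0% | 0.3% | 29.3% |

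At smaller SDs of 0.4 to 0.5 the last column is 62 to 94%.

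**3. False positives.** Simulation of 4,000 trials per setting, SD 0.6 to 1.0, left-right correlation 0.3 to 0.8, on an unbounded scale and on a bounded 0 to 4 scale. The SAP rule applied to one side rejects a true null in 1.9 to 5.3% of trials, so there is no inflation per test. A t test on the left-right mean rejects in 3.9 to 6.2%.

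**4. One value per subject.** Power per test at mean -1.0, SD 0.8 (bounded scale in brackets):

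| Left-right correlation | SAP rule, one side | t test, left-right mean |
|---|---|---|
| 0.3 | 67.9% (61.5%) | 83.0% (78.7%) |
| 0.6 | 67.3% (62.6%) | 75.8% (72.3%) |
| 0.8 | 67.1% (62.5%) | 71.2% (68.7%) |

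The gain comes from averaging the sides. At correlation 0.6 the SAP rule applied to subject means gives 76.1% (72.5%), so removing the pretest leaves power essentially unchanged. What its removal brings is an interval in every non-degenerate case.

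**5. Floor of the exact test.** With six non-zero changes the smallest two-sided exact signed-rank p is 2/2⁶ = 0.031.

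**The case against.** The strongest reply is that little is lost. Mean, SD and the full frequency table appear on both branches, so a reader can rebuild the interval as mean ± 2.571 x SD/√6. That stands. It would be wrong to infer that some cells are reported by rank sums only. What is missing is the planned interval, and a rebuilt one would be an unplanned analysis of data that the SAP's own rule has just classed as non-normal.

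Second, the SAP is not silent on sides. The 7.6 lead-in covers all efficacy analyses, and protocol 9.3.1 uses the same left/right-by-region breakdown. That is the natural reading. It still concerns summaries, 4.5.1 names the region, and 7.6.1.1 does not say which governs the test. The table shells in SAP Module 2 were not available and may settle the layout.

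Third, a reader might infer inflated error. Entering the two sides as independent observations would raise it to about 7 to 16% at correlations of 0.3 to 0.8, but nothing in the documents says to do this. A reader might also infer that a study decision depends on the p-value. The interim decision in protocol 9.4 and SAP 6.4 rests on whether MRI and biopsy show changes.

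Fourth, any figure for how often the cells come out in different forms depends on the assumed SD. If changes are only 0 or -1, all cells take the Wilcoxon branch and the forms are not mixed at all. That stands too, but it removes the interval from every cell.

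**Conclusion.** The point holds at a moderate level. The pretest in SAP 7.6.1.1 is a stated rule that makes the primary interval depend on the tie pattern of about six integers. Under the assumed SDs of 0.6 to 1.0, roughly 29 to 65% of cells would have no listed CI. The rule is undefined when all changes are equal (0.3 to 4.5% of cells in the same settings), and it leaves open a choice that moves p from 0.046 to 0.125 in a plausible cell. The unit of the test can be inferred but is not expressly stated.

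The consequence is for the precision and consistency of the primary estimate. The documents do not support a claim of inflated per-test error on the by-side reading, of a missing estimate, or of a compromised decision.

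The percentages rest on assumed distributions and on six subjects per region. The SAP's Evaluable Population lacks the 18 March 2020 restriction in protocol 9.2, so the count could be higher under the SAP's definition.

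Two neighbouring mismatches are separate: tests in the SAP against descriptive analysis in protocol 9.3.1, and the interim trigger in SAP 6.4 against protocol 9.4. SAP Section 8 says that it was prepared from the original protocol and Amendment 1. Both should be reconciled when it is updated.

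**What to change.** Change SAP 7.6.1.1 as follows, and let 7.6.2 inherit it:

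1. Remove Shapiro-Wilk as a gate. Always report mean change with 95% CI by region, from a paired t analysis named in advance.
2. Use one value per subject, the mean of the left and right changes, which matches the region-level endpoint in 4.5.1. State what is done if one side is missing. Keep side-specific results descriptive, in line with SAP 7.6 and protocol 9.3.1.
3. If all subject values are equal, report that value without CI or p-value.
4. If a signed-rank p-value is kept, label it supportive and compute it exactly. Note that at n = 6 it cannot fall below 0.031 and may disagree with the t-based CI.

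**Cost.** SAP wording and minor programming. Side-specific p-values are dropped. In the setting with mean -1.0, SD 0.8 and correlation 0.6, two region tests give at least one positive in 94.0% of trials, against 97.4% for four side tests. In the same setting the t-based CI excludes 0 while the exact p exceeds 0.05 in 41% of trials, so point 4 needs its caveat. The t interval on averaged ordinal scores at n = 6 is approximate, with a half-width of 2.571/√6 = 1.05 SD.

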2. STUDY OBJECTIVES AND ENDPOINTS

The primary, secondary, and tertiary objectives and corresponding endpoints are outlined in Table 1 below.

Table 1: Objectives and Endpoints

Objectives	Endpoints
Primary	

To assess the subject reported impact of CCH in the treatment of cellulite in adult females.	
The change from baseline (screening) in Patient-reported Photonumeric Cellulite Severity Scale (PR-PCSS) at Day 71.
Secondary	

To assess the subject and clinician reported impact of CCH in the treatment of cellulite in adult females.	
The change from baseline (screening) in PR-PCSS at Days 22 and 43.The change from baseline (screening) in Clinician-reported Photonumeric Cellulite Severity Scale (CR-PCSS) at Days 22, 43, and 71.The change from baseline (screening) in Hexsel Cellulite Severity Scale (CSS) at Days 22, 43, and 71.

To radiologically assess the impact of treatment with CCH in adult females with cellulite.	
Comparison of baseline (screening) MRI tissue morphology and septae under the treatment areas to images taken at Day 71.

To evaluate tissue histopathology to assess the impact of treatment with CCH in adult females with cellulite.	
Comparison of baseline (screening) histopathology to the histopathology of samples taken at Day 71.

To assess the safety of CCH treatment of cellulite in adult females.	
The proportion of subjects reporting each adverse event (AE), treatment-emergent adverse event (TEAE), adverse event of special interest (AESI), and serious adverse event (SAE).

Objectives	Endpoints
	
 The change from baseline in vital signs and clinical laboratory parameters at each visit where these parameters are measured. The change from baseline in anti-AUX-I and anti-AUX-II antibodies and neutralizing antibodies at each visit where these parameters are measured.
Tertiary	

 To assess the complete loss of patient reported impact after CCH treatment in adult females with cellulite. 	
 The proportion of subjects with no change (or worsening) from baseline (screening) in PR-PCSS rating at Day 161 and at Day 251.

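### The SAP's signed-rank fallback implies a normal-approximation p-value in cells of about 6 women, where it can fall below 0.05 although the exact p-value does not; the exact p should be named

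*SAP*

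**What the plan says.** - **Endpoint and scale.** The primary endpoint in SAP section 2 is "The change from baseline (screening) in Patient-reported Photonumeric Cellulite Severity Scale (PR-PCSS) at Day 71". SAP 3.12.2.1 describes the scale: "The ratings range from 0 (None) to 4 (Severe) with labels and descriptors to aid the subject in the assessments". Changes are therefore whole numbers, and ties and zeros are to be expected.
- **Test.** SAP 7.6.1.1 says "the PR-PCSS ratings at Day 71 will be compared with Baseline ratings using paired *t* test". If Shapiro-Wilk gives p of 0.05 or less, it switches to the Pratt-Lehmann signed-rank test, "adjusted for the correction factor for ties and zeros, if present", and reports the two rank sums and a p-value. It does not say whether that p-value is exact or asymptotic, and it mentions no continuity correction.
- **Level.** SAP 6.1: "All statistical tests of efficacy parameters will be 2-sided with a significance level of" 0.05.
- **Cells.** SAP 7.6: "Efficacy parameters will be summarized by treatment area (left or right) and treatment region (buttock or thigh) using the Evaluable Population". SAP 3.3: "6 subjects will be treated in the buttocks and 6 subjects will be treated in the thighs". The SAP follows protocol amendment 1, but protocol 4.1 (amendment 3) still bases efficacy on 12 women with the same intended region split.
- **Reach.** SAP 7.6.2 says of the later comparisons that ratings "will be compared with Baseline ratings using similar analysis as mentioned for primary endpoint". That adds 8 tests: PR-PCSS at 2 visits, CR-PCSS at 3 and Hexsel total at 3.
- **Protocol.** Protocol 9.3.1 plans descriptive statistics only for these endpoints.

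**The concern.** A correction factor for ties and zeros adjusts the variance of the signed-rank statistic so that it can be referred to a normal curve. An exact sign-flip p-value needs no such factor, because ties and zeros are already in the ranks. The natural reading is therefore a large-sample p-value in cells of about 6.

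The exact distribution there is very coarse. If k women change, the smallest possible two-sided exact p is 2/2^k. The normal curve does not respect that floor, so a cell can be reported as significant on data that do not reach 5% by exact calculation. The test is also used only on data that have failed Shapiro-Wilk, which a 5-level scale will often produce. The primary result and the 8 secondary comparisons would carry the same defect, although the enumeration below speaks most directly to PR-PCSS and CR-PCSS, because the Hexsel total has a wider range.

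**Working it through.** The documents give no p-value, effect size or power for this test, so there is no plan figure to reproduce.

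**Inputs.** n = 6 per cell (SAP 3.3 with 7.6); integer changes (SAP 3.12.2.1); two-sided 0.05 (SAP 6.1); fallback when Shapiro-Wilk p ≤ 0.05 (SAP 7.6.1.1).

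**Formulas.** Rank the absolute changes with zeros included, then drop the ranks of the d0 zeros. W is the negative rank sum and t the size of each tied group of non-zero changes.
- E = [n(n+1) − d0(d0+1)]/4
- V = [n(n+1)(2n+1) − d0(d0+1)(2d0+1)]/24 − Σ(t³ − t)/48
- z = |W − E|/√V, or (|W − E| − 0.5)/√V with a continuity correction
- Exact p: the share of the 2^k sign patterns of the k non-zero ranks that are at least as extreme.

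**Five improved by one level, one unchanged.** W = 20; E = (42 − 2)/4 = 10; V = (546 − 6)/24 − 120/48 = 22.5 − 2.5 = 20. z = 10/√20 = 2.236, p = 0.0253. With continuity correction, z = 9.5/√20 = 2.124, p = 0.0336. Exact p = 2/2^5 = 0.0625. Shapiro-Wilk p < 0.001, so the fallback applies.

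**Four improved by one level, two unchanged.** W = 18; E = (42 − 6)/4 = 9; V = (546 − 30)/24 − 60/48 = 21.5 − 1.25 = 20.25. z = 9/4.5 = 2.00, p = 0.0455. With continuity correction, z = 8.5/4.5 = 1.889, p = 0.0589. Exact p = 2/2^4 = 0.125. Shapiro-Wilk p = 0.0014.

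**General pattern.** With k equal changes in one direction, z reduces to √k and the exact p is 2/2^k, whatever the number unchanged:

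| k | approximate p | exact p |
|---|---|---|
| 4 | 0.0455 | 0.125 |
| 5 | 0.0253 | 0.0625 |
| 6 | 0.0143 | 0.0312 |
| 8 | 0.0047 | 0.0078 |

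**All patterns at n = 6.** There are 210 unordered patterns of changes from -2 to +2, of which 110 fail Shapiro-Wilk. Without a continuity correction, 24 of these have approximate p ≤ 0.05, and 14 of the 24 have exact p > 0.05. With one, it is 8 of 18. Patterns in which all women change equally have no defined Shapiro-Wilk result and are left out.

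**Five women.** Dropouts are not replaced (SAP 4.1.1 and 4.1.2). With 5 women no exact two-sided p can fall below 2/2^5 = 0.0625, yet 12 fallback patterns have approximate p ≤ 0.05 without a continuity correction.

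**False-positive rates at n = 6, no continuity correction.** The null distributions are assumptions, symmetric about zero.

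| Null distribution of change | given fallback | whole procedure |
|---|---|---|
| 0: 0.4; ±1: 0.3 each | 11.3% | 5.05% |
| 0: 0.2; ±1: 0.4 each | 7.8% | 5.5% |
| 0: 0.4; ±1: 0.25; ±2: 0.05 each | 8.0% | 5.15% |
| 0: 0.3; ±1: 0.25; ±2: 0.1 each | 8.9% | 6.3% |
| 0: 0.6; ±1: 0.2 each | 4.2% | 2.0% |
| 0: 0.7; ±1: 0.15 each | 1.5% | 0.8% |

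With a continuity correction the rates given fallback are 0.1% to 3.5%. The exact test gives 0% to 1.4% under the first four nulls.

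**The case against.** - **The asymptotic reading is inferred.** This stands as a limit. If the programmer meant something else, the p-value is undefined in the SAP, and the same sentence cures that.
- **The four-improved example is fragile.** This stands. It needs equal changes and no continuity correction. If one of the four improves by two levels and the rest by one, Shapiro-Wilk p is 0.21 and the t test is used instead. The five-improved case holds with or without the continuity correction.
- **The 5% level is not broken.** A reader might infer from the 11.3% figure that the SAP's two-sided 5% level fails. The documents do not support that. SAP 6.1 sets the level for the test of each parameter, not for one branch, and the full t-or-Pratt procedure runs at 0.8% to 6.3%. Zero-heavier nulls also bring the fallback rate below 5%.
- **The cell size may be larger.** SAP 7.6 speaks of summaries by side and region, 7.6.1.1 does not say that tests run in each cell, and SAP 4.5.1 defines the change for the whole region. With 12 values treated as independent, the rate given fallback is 4.2% to 7.7%, and 8 improved with 4 unchanged gives 0.0047 against an exact 0.0078. The gap shrinks, and the SAP should say which unit it tests.
- **Little depends on the p-value.** The study is open-label and uncontrolled, with no formal sample size calculation; the interim rule turns on MRI and biopsy; counts and listings would show how many women improved. This limits the weight of the point but does not make a misleading p-value acceptable once the SAP commits to reporting it.

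**Conclusion.** The point holds in a limited form. As worded, the fallback implies a normal-approximation p-value, and in cells of about 6 it can fall below 0.05 when the exact p-value does not. The firmest case is five improved by one level and one unchanged: 0.0253, or 0.0336 with a continuity correction, against 0.0625. It is not an isolated pattern, since 14 of 24 nominally significant fallback patterns (8 of 18 with the correction) share the problem.

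This rests on three assumptions: that the p-value is asymptotic, that tests are run within side-by-region cells, and, for the patterns counted, that changes lie between -2 and +2. The error is in individual reported p-values rather than in a clear failure of the overall level. A reader might also conclude that four improved and two unchanged will be reported as significant. That follows only with equal changes and no continuity correction, and the SAP leaves the latter open.

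**What to change.** Add to SAP 7.6.1.1 that the Pratt signed-rank p-value is the exact conditional p from enumerating the 2^k sign patterns of the non-zero ranks, and drop the reference to a correction factor. Section 7.6.2 takes this over by its existing cross-reference. The cost is one sentence and a few lines of code: at n = 6 there are at most 2^6 = 64 patterns, and no new data are needed.

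The price is conservatism. In a cell of 6, an exact p below 0.05 needs all six women to change in the same direction (2/2^6 = 0.03125). If all six change by the same amount, Shapiro-Wilk is undefined, so the SAP should also say which test then applies. Because so few outcomes can reach 5%, the SAP should present these p-values as supportive of the descriptive summaries planned in protocol 9.3.1.
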